## **Group (B) Proprioceptive neuromuscular facilitation (PNF)**

In the PNF group, scapular PNF will be applied by a trained therapist in two diagonals, anterior elevation and posterior depression (Fig. 22A and 22B, respectively) and posterior elevation and anterior depression (Fig. 22C and 22D, respectively) for three sets of 10 repetitions, The rest interval between repetitions will be 20 seconds (Mtaspinar et al., 2013; Park et al., 2008).

[figure not shown]
**Figure 16 A) Anterior elevation of the scapula, B) posterior depression of the scapula, C) posterior elevation of the scapula, D) anterior depression of the scapula**

Patients will lay on the unaffected side while the therapist stands in the line of desired motion. Firstly, the therapist will give preparatory instructions. In the beginning of the pattern, the therapist pulls the scapula to the elongated position and then gives instructions for the desired movement.

Rhythmic initiation and repeated contractions facilitation techniques will be applied in all patterns. The rhythmic initiation technique teaches the motion, helps the patient to relax, improves coordination, and normalizes the motion. The repeated contractions technique increases active range of motion and strength and guides the patient's motion towards the desired motion. (Mtaspinar et al., 2013; Park et al., 2008). Description of each scapular PNF pattern is described below

### **Scapular anterior elevation (Fig. 23A and 23B)**

[figure not shown]
- Muscles: levator scapulae, rhomboids, serratus anterior
- Positioning: sidelying with hips/knees flexed appropriately
- Grip: overlapping fingers on anterior aspect of GH joint and acromion
- Sequence: pull scapula down and back into posterior depression so anterior-lateral neck muscles are taut; don't pull so far that you lift patient's head; no trunk rotation
- Command: "Up"
- Movement: scapula moves up and slightly anterior
- Body Mechanics: arms relaxed; provide resistance by shifting weight from back to front leg
- Resistance: arc following curve of patient's body

**Figure 17 SCAPULAR ANTERIOR ELEVATION**

### **Scapular posterior depression (Fig.24A and 24B)**

- Muscles: lower serratus anterior, rhomboids, latissimus
- Positioning: sidelying with hips/knees flexed appropriately
- Grip: heels of hands along vertebral border of scapula with one hand just above (cranial to) the other and fingers on scapula pointing towards acromion
- Sequence: push scapula up and forward into anterior elevation until posterior muscles below the spine of the scapula are taught; no trunk rotation
- Command: “Down”
- Movement: scapula moves down and slightly posterior
- Body Mechanics: arms relaxed; provide resistance by shifting weight from front to back leg
- Resistance: arc following curve of patient’s body

**Figure 18 SCAPULAR POSTERIOR DEPRESSION**

### **Scapular posterior elevation (Fig. 25A and 25B)**

[figure not shown]
- Muscles: trapezius, levator scapulae
- Positioning: sidelying with hips/knees flexed appropriately
- Grip: overlapped hands posteriorly on upper trapezius muscle, superior to scapular spine
- Sequence: push scapula down and slightly forward into anterior depression so posterior-lateral neck muscles are taut; don't push so far that you lift patient's head; no trunk rotation
- Command: "Up"
- Movement: scapula moves up and slightly posterior
- Body Mechanics: arms relaxed; provide resistance by shifting weight from front to back leg
- Resistance: arc following curve of patient's body

**Figure 19 SCAPULAR POSTERIOR ELEVATION**

### **Scapular Anterior Depression (Fig. 26A and 26B)**

- Muscles: rhomboids, serratus anterior, pectoralis minor/major
- Positioning: sidelying with hips/knees flexed appropriately
- Grip: hands on anterior and posterior axilla with fingers pointing toward opposite hip
- Sequence: lift scapula up and back into posterior elevation; don't push so far that you lift patient's head; no trunk rotation
- Command: "Down"
- Movement: scapula moves down and slightly anterior
- Body Mechanics: arms relaxed; provide resistance by shifting weight from back to front leg
- Resistance: arc following curve of patient's body

**Figure 20 SCAPULAR ANTERIOR DEPRESSION**

## **Statistical analysis**

- Data will be analyzed using the statistical package for social science (SPSS) program, version 27 (SPSS Inc, Chicago, IL, USA).
- Descriptive statistics will be used to summarize the data. Data will be reported as mean  $\pm$  SD for quantitative variables and frequency distribution (%) for categorical variables.
- The normality of data will be checked using Shapiro–Wilk test.
- Levene’s test will be used to check the homogeneity between groups.
- Two-way Multiple Analysis of Variance (MANOVA) will be conducted to compare the mean values of the measured variables of the three groups.
- The level of significance for all statistical tests will be set at  $\alpha = 0.05$ .

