### **Purpose of the study:**

The purpose of this study is to compare the effect of scapular muscle strengthening versus PNF exercise on scapular muscle strength, scapular muscles ratio, scapular asymmetry, pain, and function in patients with shoulder impingement syndrome.

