### **Hypotheses of the study:**

1. There will be no significant difference between scapular muscle strengthening and PNF exercise on improving muscle strength of upper trapezius in patients with shoulder impingement syndrome.

2. There will be no significant difference between scapular muscle strengthening and PNF exercise on improving muscle strength of middle trapezius in patients with shoulder impingement syndrome.
3. There will be no significant difference between scapular muscle strengthening and PNF exercise on improving muscle strength of lower trapezius in patients with shoulder impingement syndrome.
4. There will be no significant difference between scapular muscle strengthening and PNF exercise on improving muscle strength of serratus anterior in patients with shoulder impingement syndrome.
5. There will be no significant difference between scapular muscle strengthening and PNF exercise on muscle ratio of upper trapezius/lower trapezius muscles in patients with shoulder impingement syndrome.
6. There will be no significant difference between scapular muscle strengthening and PNF exercise on muscle ratio of upper trapezius/middle trapezius muscles in patients with shoulder impingement syndrome.
7. There will be no significant difference between scapular muscle strengthening and PNF exercise on muscle ratio of upper trapezius/serratus anterior muscles in patients with shoulder impingement syndrome.
8. There will be no significant difference between scapular muscle strengthening and PNF exercise on scapular symmetry at 0° abduction in patients with shoulder impingement syndrome.
9. There will be no significant difference between scapular muscle strengthening and motor control exercise on scapular symmetry at 45° abduction in patients with shoulder impingement syndrome.
10. There will be no significant difference between Scapular muscle strengthening and motor control exercise on scapular symmetry at 90° abduction in patients with shoulder impingement syndrome.

11. There will be no significant difference between scapular muscle strengthening and PNF exercise on improving pain in patients with shoulder impingement syndrome.
12. There will be no significant difference between scapular muscle strengthening and PNF exercise on improving function in patients with shoulder impingement syndrome.

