## Sample size calculation:

In order to detect an effect size of Cohen's  $d = 0.80$  with 80% power ( $\alpha = 0.05$ ), G\*power software (version 3.1.9.7; Franz Faul, Universitat Kiel, Germany) suggests we will need 64 participants, however, we will aim to recruit 66 subjects to have equal groups representation (22 per group) using analysis of variance (ANOVA) test as shown in the (figure 7).

[figure not shown]

Figure 1 ample size calculation

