## Subjects:

Sixty-six male and female patients, with age between 20-50 years, diagnosed with SIS will be recruited through direct referrals, thus, a sample of convenience will be used. They will be asked to sign the informed consent

form (**Appendix I**). Participants will be randomly allocated to three experimental groups as follow:

**Group A** (n=22): will receive a program of scapular muscle strengthening exercises for 18 sessions (3 sessions per week for six weeks)

**Group B** (n=22): will receive a scapular PNF exercise program for the same frequency as in group A

**Group C** (n=22): will be a control group who will not receive any treatment during the study period.

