## **Shoulder pain and disability index (Appendix II):**

Self-report questionnaire developed to measure the pain and disability associated with shoulder pathology. The SPADI consists of 13 items in two subscales: pain (five items) and disability (eight items).

The pain dimension consists of five questions regarding the severity of an individual's pain. Functional activities are assessed with eight questions designed to measure the degree of difficulty an individual has with various activities of daily living that require upper-extremity use. The SPADI takes 5 to 10 minutes for a patient to complete and is the only reliable and valid region-specific measure for the shoulder **(Roash al., 1991)**.

Patients asked to mark the appropriate point on the scoring system of the questionnaire, which represented their status of shoulder pain and disability. Total pain score:  $/ 50 \times 100 = \%$ , Total disability score:  $/ 80 \times 100 = \%$  and Total SPADI score:  $/ 130 \times 100 = \%$  Higher score on the SPADI is indicative of higher pain and/or disability **(Breckenridge al., 2011)**.

Psychometric Properties the SPADI :MDC: 18 point (MDC 95%) with  $ICC \geq 0.89$ , The MCID has been reported to be 8 points; this represents the smallest detectable change that is important to the patient **(Paul et al 2004)**.

No large floor or ceiling effects for the SPADI have been observed **(Bot et al 2004, Roy et al 2009)**.

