## **Assessment procedure**

Assessment procedure will be performed before and after the treatment. The following procedure will be conducted

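### The one between-group test stated is a three-group MANOVA, but the purpose and hypotheses compare the two active programmes outcome by outcome; a baseline-adjusted A–B contrast would answer them at little cost

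*Protocol*

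**What the plan says.** The aim, under Purpose of the study, is "to compare the effect of scapular muscle strengthening versus PNF exercise on scapular muscle strength, scapular muscles ratio, scapular asymmetry, pain, and function". Hypotheses of the study then lists 12 statements, each on a single outcome and each comparing strengthening with another active programme. Number 11 is typical: "There will be no significant difference between scapular muscle strengthening and PNF exercise on improving pain in patients with shoulder impingement syndrome". Ten of the 12 name PNF. Numbers 9 and 10 (scapular symmetry at 45° and 90°) name motor control exercise, which no arm receives. None of the 12 mentions group C, which "will be a control group who will not receive any treatment during the study period" (Subjects).

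The two places that name a between-group test point elsewhere. Sample size calculation aims "to have equal groups representation (22 per group) using analysis of variance (ANOVA) test". Statistical analysis says "Two-way Multiple Analysis of Variance (MANOVA) will be conducted to compare the mean values of the measured variables of the three groups". The second factor of the two-way model is not named. Shapiro–Wilk and Levene appear only as assumption checks. "The level of significance for all statistical tests will be set at" 0.05.

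On the data available, Assessment procedure says "Assessment procedure will be performed before and after the treatment", so each outcome has a baseline value.

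**The concern.** An omnibus three-group test asks whether any group differs from any other. It can be significant only because untreated patients did worse, which says nothing about strengthening versus PNF. A multivariate version also does not say which outcome differs, although every hypothesis concerns one outcome. In the other direction, a real A–B difference can be missed when C lies between the two active arms.

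The hypotheses are worded as the absence of a significant difference. With no A–B estimate or interval planned, a non-significant result is likely to be read as showing that the programmes are equal.

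If *two-way* means group by time, the A–B part of that model is a comparison of change scores. That is valid, but it uses the baseline less efficiently than adjusting the post-treatment value for it.

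**Working it through.** **Inputs.** From Sample size calculation: 22 per group, three groups, α = 0.05, d = 0.80, target power 80%. The pre–post correlation r is not in the protocol and is taken as 0.3, 0.5, 0.7 and 0.8. Outcomes have SD 1.

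**1. The plan's own figure.** Sixty-four participants reproduces as a three-group omnibus F test with f = d/2 = 0.40 and λ = f²N. At N = 64, λ = 0.16 × 64 = 10.24 and power is 80.5%; at N = 63 it is 79.8%. So the sizing also targets any difference among three groups. For A versus B alone at d = 0.80, 22 per arm with error pooled over the three arms (63 df) gives 74.3%.

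**2. A = B, with C 0.8 SD away (one outcome).** λ = 22·Σ(m − m̄)²/sd². With means (0, 0, 0.8), Σ(m − m̄)² = 0.4267 and λ = 9.39. The F test (2 and 63 df) on post-treatment values rejects in 76.8% of trials. For group by time, sd² = 2(1 − r), and it rejects in 61/77/94/99% at r = 0.3/0.5/0.7/0.8.

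**3. A–B = 0.80 SD, with C midway (one outcome).** With means (0, 0.8, 0.4), Σ(m − m̄)² = 0.32 and λ = 7.04. The omnibus F on post-treatment values has 63.6% power. The A–B contrast uses noncentrality (0.8/sd)·√(22/2). Here sd = 1 for unadjusted post-treatment values, √(2(1 − r)) for change scores (63 df) and √(1 − r²) for ANCOVA (62 df).

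| r | Omnibus group × time | A–B change score | A–B ANCOVA | A–B ANCOVA at 0.05/12 |
|---|---|---|---|---|
| 0.3 | 49% | 60% | 78% | 43% |
| 0.5 | 64% | 74% | 85% | 54% |
| 0.7 | 86% | 92% | 96% | 77% |
| 0.8 | 96% | 98.5% | 99% | 92% |

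The unadjusted A–B contrast stays at 74% whatever r is. Simulation (40,000 trials per setting) gave ANCOVA power of 77.4/84.9/95.1/99.1% and type I error of 4.9–5.1% for the change-score and ANCOVA contrasts. ANCOVA reaches 80% from r of about 0.36 by formula (0.38 by simulation), and change scores from about 0.57.

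**4. The multivariate test itself.** Steps 2 and 3 use one outcome. A one-way Pillai test was also simulated on 12 post-treatment outcomes with between-outcome correlation assumed at 0.3 or 0.5. With A and B identical and both 0.8 SD from C on every outcome, it rejected in 71% or 46–48% of trials. With A–B = 0.8 SD on one outcome only and C midway, it rejected in 24–27% or 35–36%.

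**5. Multiplicity.** Twelve A–B tests at 0.05 carry a family-wise error of 1 − 0.95¹² = 46% if independent. The last column of the table shows what Bonferroni costs.

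**6. What an A–B interval could show on SPADI.** Shoulder pain and disability index gives an MDC95 of 18 points, an ICC of at least 0.89, and "The MCID has been reported to be 8 points". Assume the MDC and ICC come from one sample and that its SD applies here. Then SEM = 18/(1.96·√2) = 6.49, and SD is at least 6.49/√0.11 = 19.6. The 95% half-width by ANCOVA is 1.999 × 19.6 × √(2/22) × √(1 − r²), which is 11.3/10.2/8.4 points at r = 0.3/0.5/0.7. It falls below 8 only when r exceeds about 0.74.

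**The case against.** Follow-up contrasts, covariates and multiplicity rules are often left to a statistical analysis plan, and an omnibus test followed by pairwise comparisons is a standard sequence. That limits the point to what the protocol does state: the test it names does not match the hypotheses it names. That mismatch remains.

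The loss of power also depends on where C lies, and C midway means one active programme does worse than no treatment. On unadjusted post-treatment values with A–B = 0.8 SD, requiring both the omnibus and the A–B test to reject costs about 12 points with C midway (62% against 74%). It costs about 6 points with C level with the lower active arm (69% against 74%), and under 1 point with C 0.4 SD below both. So the risk of missing a difference is small if both programmes clearly beat no treatment. This does not touch the other half of the point: a significant omnibus result need not mean that A differs from B.

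The one-outcome percentages are illustrative, because the plan is multivariate. The 12-outcome simulation shows the same direction with different values.

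Finally, ANCOVA over change scores is a gain in efficiency and not the repair of an error. The gain is about 3 points at r = 0.7 and under 1 at 0.8, but about 18 points at r = 0.3.

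**Conclusion.** The concern holds as an inexpensive improvement. The stated test answers whether any of three groups differ on any outcome, while the purpose and all 12 hypotheses ask about two active programmes on one outcome each. On one outcome, the omnibus test is significant in 77% of trials when A and B are identical and C is 0.8 SD away. When A and B differ by 0.80 SD with C midway, it has 64% power on post-treatment values, against 78–96% for a baseline-adjusted A–B contrast at r = 0.3–0.7. These figures assume normal outcomes, 22 completers per arm, the stated positions of C, and a pre–post correlation that the protocol does not give. Even the better analysis will probably leave a SPADI interval that does not exclude 8 points, so this sample size does not support a claim that the two programmes are equal.

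**What to change.** Replace the MANOVA line with the following.

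- For each outcome, fit an ANCOVA of the post-treatment value on group (three levels) and that outcome's baseline. The A–B contrast with its 95% confidence interval is the main result; A–C and B–C are secondary.
- Name one primary outcome and test its A–B contrast at 0.05, with the other 11 outcomes secondary. Alternatively, apply Holm across the 12 A–B tests.
- State that a non-significant A–B result is not evidence of no difference, and read the SPADI interval against the 8-point MCID.
- Reconcile the comparator named in hypotheses 9 and 10 with the arms of the trial.

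This takes a few lines in the analysis section and uses the same data, visits and software, with slightly more analysis work. The real cost is power per outcome if error is controlled across all 12: with Bonferroni, 43/54/77/92% at r = 0.3/0.5/0.7/0.8. Naming one primary outcome avoids that loss for that outcome.

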#### **Randomization:**

Patients will be randomly assigned into one of the three groups. We will use a simple randomization method to allocate participants to the groups. A random number generator available online from [www.randomization.com](http://www.randomization.com) will be used.

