## **3. Lateral Scapular Slide test**

Subjects will be standing with both arms at the sides, in glenohumeral joint neutral. The inferior-most aspect of the inferior angle of the scapula and the adjacent spinous process of the reference vertebra in the same horizontal plane will be identified through palpation and will be marked with marker pen by the examiner as shown in **Figure 18**.

For test position 2 – subject will actively place both hands on the ipsilateral hips (in medial rotation) at 45° of abduction in the coronal plane **Figure 19**.

Position 3 - subject will actively extend both elbows and place the upper extremities in a position of maximum medial rotation at 90° of abduction in the coronal plane **Figure 20**.

[figure not shown]
Measurements will be taken with a vernier caliper from the inferior angle of scapula to adjacent spinous process of reference vertebra. The examiner will obtain the measurements bilaterally.

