**Figure 12 LSST position 1- arm at the sides**

**Figure 13 Position 2 both hands on ipsilateral hips**

**Figure 14 Position 3 of abduction 90° and medial rotation**

#### **4. Shoulder pain and disability index**

Patients is asked to circle the number that best describes his/her level of pain or dysfunction of the questionnaire (**Appendix II**). This represents their status of shoulder pain and disability. Total pain score: / 50 x 100 = %, Total disability score: / 80 x 100 = % and Total SPADI score: / 130 x 100 = % Higher score on the SPADI is indicative of higher pain and/or disability

This index will be scored before and after the treatment procedure to measure the function and pain on patients with SIS.

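### The two-way MANOVA on before-and-after data names neither its second factor nor a within-patient time term and makes no stated use of baseline; fitted as a plain factorial, its tests use the wrong error

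*Protocol*

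**What the plan says.** The Statistical analysis section gives one inferential method: "Two-way Multiple Analysis of Variance (MANOVA) will be conducted to compare the mean values of the measured variables of the three groups". It names no factor other than group. It says nothing of time, repeated measures, change or baseline.

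The data are paired. Under Assessment procedure: "Assessment procedure will be performed before and after the treatment". The SPADI section repeats this for pain and function: "This index will be scored before and after the treatment procedure to measure the function and pain on patients with SIS".

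The Randomization section names no stratification factor: "Patients will be randomly assigned into one of the three groups. We will use a simple randomization method to allocate participants to the groups". The Sample size calculation rests on 64 patients, raised to 66 (22 per group), "using analysis of variance (ANOVA) test", with no repeated-measures element mentioned.

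In the Hypotheses, items 1 to 4, 11 and 12 concern improvement in strength, pain and function. Items 5 to 10 concern muscle ratios and scapular symmetry and do not use that word.

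**The concern.** Group is one factor of the two-way model. With no stratifier, the evident candidate for the other is time, which repeats within patients. In its ordinary form a two-way MANOVA has between-patient factors only and one pooled error. Applied to stacked before and after values, it would count 2 × 66 = 132 rows as 132 independent patients.

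The two tests of interest would then fail in opposite directions. The group test would be too liberal, because a patient's two values move together. The group-by-time test, which addresses improvement, would be too conservative and would lose power. All twelve hypotheses are worded as no difference, so a test that seldom rejects would look like support for them.

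A second problem does not depend on how the error is built. A comparison of group means over both assessments includes the baseline, where randomised groups differ only by chance.

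**Working it through.** **Inputs from the protocol.** Three groups of 22; two assessments per patient; α = 0.05; Cohen's d = 0.80; 80% power.

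**Assumptions not in the protocol.** Pre-post correlation ρ, shown over 0.3/0.5/0.7/0.9; equal variances σ² at both assessments; no dropout. For power, one arm is 0.8 SD better at follow-up and the other two are unchanged.

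**The plan's own figure.** Reading d = 0.80 as f = d/2 = 0.40, a three-group ANOVA has noncentrality N·f². At N = 64 this is 64 × 0.16 = 10.24, giving 80.5% power; at N = 66 power is 81.8%. The stated 64 reproduces and is not in dispute.

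**Null rejection under a plain factorial.** There are six cells of 22, so error df = 132 − 6 = 126, and the critical value of F(2,126) is 3.07.
- A patient's average over the two assessments has variance σ²(1+ρ)/2. The model assumes σ²/2, so the group F is inflated by (1+ρ). Rejection rate ≈ P(F(2,126) > 3.07/(1+ρ)).
- A patient's change has variance 2σ²(1−ρ). The model assumes 2σ², so the group-by-time F is deflated by (1−ρ). Rejection rate ≈ P(F(2,126) > 3.07/(1−ρ)).

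At ρ = 0.5 the effective thresholds are 3.07/1.5 = 2.05 (13.4%) and 3.07/0.5 = 6.14 (0.3%).

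| ρ | Group, true null | Group-by-time, true null |
|---|---|---|
| 0.3 | 9.9% | 1.4% |
| 0.5 | 13.4% | 0.3% |
| 0.7 | 16.9% | 0.01% |
| 0.9 | 20.3% | about 0% |

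A simulation of 20,000 trials gave 9.7%/13.2%/16.9%/21.0% for group and 1.4%/0.3%/0.02%/0% for group-by-time. With time within patient, both tests stayed near 5%. At ρ = 0 the two models agree.

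**Power, one arm 0.8 SD better at follow-up.** The between-group sum of squares is 22 × 0.8² × 2/3 = 9.387 in units of σ².
- Mixed model, group-by-time, F(2,63): λ = 9.387/[2(1−ρ)] = 6.70/9.39/15.64/46.93.
- Follow-up adjusted for baseline, F(2,62): λ ≈ 9.387/(1−ρ²) = 10.32/12.52/18.41/49.40. This exceeds the mixed-model λ by the factor 2/(1+ρ), so it is more powerful whenever ρ is below 1.
- Mixed model, group main effect, F(2,63): the expected difference in the before/after average is (0 + 0.8)/2 = 0.4 SD, so λ = (9.387/4)/[(1+ρ)/2] = 3.61/3.13/2.76/2.47.

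| ρ | Plain factorial, group-by-time (simulated) | Time within patient, group-by-time | Follow-up adjusted for baseline | Correct mixed model, group main effect |
|---|---|---|---|---|
| 0.3 | 43% | 61% | 80% | 36% |
| 0.5 | 39% | 77% | 88% | 32% |
| 0.7 | 34% | 94% | 97% | 29% |
| 0.9 | 23% | over 99% | over 99% | 26% |

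**Several outcomes together.** With a further assumed between-outcome correlation of 0.3, the plain-factorial Wilks test for group rejects a true null in 15%/23%/33% of trials for 4 outcomes and 26%/43%/64% for 12 outcomes, at ρ = 0.3/0.5/0.7 (2,000 simulated trials each). With time within patient the rates were 4.1% to 5.8%.

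**The case against.** The strongest reply is that the protocol does not describe a data layout. A reader might infer that it treats the two assessments as independent; no sentence says so. MANOVA is also a standard route to repeated measures, with before and after values entered as separate dependent variables on one row per patient, and authors do write "two-way" for a group-by-time mixed design. This stands: the error rates above are conditional on a plain factorial being fitted.

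A reader might also infer that side is a repeated factor, since for the slide test "The examiner will obtain the measurements bilaterally". The documents do not support that. A symmetry outcome needs both sides to form one score per patient and position, and nothing makes side a factor in the model.

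It may further be said that factor definitions belong in a statistical analysis plan, which is not shown. That would answer a mere omission. Here the protocol does choose a method, and as literally named the method does not fit paired data. Its stated target, group means, is also a poor one if both assessments are pooled, even with a correct error term.

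Finally, group means could be read as post-treatment means only. That reading gives a valid error, but it leaves the second factor unexplained and does not use the baseline values that are collected.

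**Conclusion.** The point holds as a conditional finding about the named method. The Statistical analysis section fixes a two-way MANOVA of group means for before-and-after data without naming the second factor, placing time within patients, or using baseline. Fitted as a plain factorial, it gives a group test that rejects a true null two to four times as often as intended for one outcome, and a group-by-time test with 23% to 43% power where a within-patient test has 61% to over 99%. These figures rest on an assumed pre-post correlation of 0.3 to 0.9, 22 per group, equal variances and no dropout; the problem vanishes only at zero correlation.

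One part needs no assumption about layout. If both assessments are pooled, the group main effect carries half of any follow-up difference, even in a correct mixed model. The documents do not support saying that the protocol treats the assessments as independent. As this is the trial's only inferential analysis, the sentence should be settled before data are analysed.

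**What to change.** Replace the MANOVA sentence in Statistical analysis with one of two specified models:
- a comparison of post-treatment values between the three groups, adjusted for the baseline value of the same outcome; this is generally the more powerful choice; or
- a mixed-design model with group between patients, time (before, after) within patients, and group-by-time as the test of the hypotheses.

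These are alternatives, not equivalents (88% against 77% power at ρ = 0.5 in the example above), so one should be named in advance. Add that the group effect averaged over time is not used for inference.

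The cost is a rewritten sentence. The data and software are unchanged, and no extra patients or visits are needed.
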